COMIRB Protocol

COLORADO MULTIPLE INSTITUTIONAL REVIEW BOARD
[name] [contact] [contact]

Protocol #: 16-1965

Project Title: Management of diabetic ketoacidosis in children: does early glargine prevent rebound hyperglycemia?

Short Title: "Early glargine in DKA"

Principal Investigator: [name]

Co-investigators: [name] [name]; [name], PhD

Version Date: 11/6/2017

I. Hypotheses and Specific Aims:

Hypothesis 1 (Primary outcome): Early administration of glargine in the treatment of DKA in children will result in reduced rebound hyperglycemia compared to those given standard-of-care management.

Specific Aim 1 (Primary outcome): To evaluate the rate of rebound hyperglycemia (serum glucose level of greater than 180 mg/dL (>10 mmol/L) within 12 hours after discontinuation of IV insulin) in children treated for diabetic ketoacidosis (DKA) with early glargine versus standard-of-care management.

Hypothesis 2: Early administration of glargine in the treatment of DKA in children will result in a reduced rate of recurrent ketogenesis compared to those given standard-of-care management.

Specific Aim 2: To evaluate the rate of recurrent ketogenesis (beta-hydroxybutyrate ≥ 1.5 mmol/L within 12 hours after discontinuation of IV insulin) in children treated for diabetic ketoacidosis (DKA) with early glargine versus standard-of-care management.

Hypothesis 3: The risk of hypoglycemia will not differ between those given early administration of glargine versus those given standard-of-care management:

- a. Early administration of glargine in the treatment of DKA in children will not increase hypoglycemic events compared to those given standard-of-care management.
- b. Rate of blood glucose decrease while on IV insulin in children with DKA will not be different between those given early administration of glargine versus those given standard-of-care management.
- c. Participants who received early glargine will not need more frequent reductions in the IV insulin rate than those given standard-of-care management.

Specific Aim 3: To determine the risk of hypoglycemia between those given early administration of glargine versus those given standard-of-care management.

- a. Assess the frequency of hypoglycemic events during treatment of DKA, and within 12 hours after discontinuation of IV insulin, in children given early glargine versus standard-of-care management.

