- If more than 12.5% dextrose IV fluids are needed to maintain serum glucose between 100 mg/dL and 200 mg/dL, the IV insulin rate will be decreased by 0.01 units/kg/hr.

Laboratory Monitoring during DKA treatment:

- Blood glucose concentration is obtained at presentation and hourly while on IV insulin using a point-of-care glucometer or serum measurements.
- Venous pH, serum electrolytes (Na, K, Cl, HCO₃, BUN, creatinine) are obtained at presentation and then every 2-4 hours while on IV insulin.
- Serum beta-hydroxybutyrate (BHB) will be obtained at presentation and then every 6 hours while on IV insulin until \leq 1.0 mmol/L.
- HbA1c will be obtained at presentation.

Continuous Glucose Monitoring (CGM): An option to have CGM sensor placed will be discussed with participant and/or primary guardian. The CGM system used during this study will be the Abbott FreeStyle Libre Pro Flash® Glucose Monitoring System (Figure 2).

Figure 2: Abbott FreeStyle Libre Pro Flash® Glucose Monitoring System:

<http://www.freestylelibrepro.us/blood-glucose-monitoring-device.html>

The FreeStyle Libre Pro® uses a small low-profile sensor approved for up to 14 days of wear in the USA by the FDA and has shown an average mean absolute relative difference (MARD) of 11.4% over 14 days of continuous wear. The Libre is also marketed as being free from interference with acetaminophen, eliminating this as a concern in our population as this is a common medication used in pediatrics. Further, this system does not require calibration and is blinded from the participant. Data will be available to study personnel at time of download after 1 week of wear.

CGM protocol:

- Following informed consent, an area on the back of the upper arm will be cleaned with an isopropyl alcohol solution and the CGM sensor system will be placed by trained study personnel.
- The CGM sensor placement will ideally occur after initial rehydration has been established, however, if this is not possible the CGM can be placed on the participant at any time during the initial 12 hours of DKA management.
- The CGM sensor will remain on the participant for the duration of hospitalization and an additional week following discharge.
- If a CGM sensor malfunctions during the participant's hospitalization, a new sensor can be replaced by study personnel as soon as possible following knowledge of the malfunction.

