- Participants will return the CGM sensor to study personnel after approximately 1 week (see section C.2.3 below).

C.2.2. Upon resolution of DKA:

- When venous pH ≥ 7.3 and serum bicarbonate ≥ 18 mmol/L (or BHB < 1.0 mmol/L) and participant is awake and alert, he/she will be transitioned to subcutaneous insulin:
 - Discontinuation of IV insulin.
 - Initial subcutaneous dosing:

- Glargine: 0.3 units/kg SQ x 1 for new onset T1D (or home glargine equivalent dose for established T1D) – if not already given as part of the Early Glargine/study group (see section C. 2.1 for dosing).
- Lispro: 0.2-0.6 units/kg/day, administered using a standard Multiple Daily Injection (MDI) regimen: before meals or as needed for hyperglycemia (but not more often than every 4 hours).
- The on-call physician can override the above dosing based on clinical judgment.
- **Insulin pump:** Participants with established T1D who are managed with an insulin pump at baseline will have the option to either:
 1. NOT reconnect or use their insulin pump for 24 hours after the protocol glargine dose was administered and will receive standard MDI therapy during that time with dosing determined by the inpatient diabetes team or study personnel. They can resume full home insulin pump use after 24 hours following glargine administration.
 2. Reconnect their home insulin pump to use for BOLUSING ONLY with meals and snacks and will not use their basal rate (set a temporary basal rate of 0%) for 24 hours after the glargine dose was administered. They can resume full home insulin pump use after 24 hours following glargine administration.

Laboratory monitoring upon resolution of DKA:

- Blood glucose concentration obtained before meals, at bedtime, and at 0200 using point-of-care glucometer.
- Serum BHB obtained every 6 hours until ≤ 1.0 mmol/L or at any time if blood glucose on glucometer is > 300 mg/dL for two consecutive measurements.
- Participants who remain hospitalized over 24 hours will have a BHB drawn at 12-18 hours after discontinuation of IV insulin to assess for late-recurrent ketosis.

Table 1: Summary of laboratory monitoring:

| Data: | During DKA | Upon resolution of DKA |
|---------------------|--|--|
| POC glucose (mg/dL) | At presentation and hourly | Before meals, at bedtime, at 0200 |
| BMP | At presentation and approx. every 2-4 hours | As needed |
| HbA1c (%) | At presentation | |
| VBG | At presentation and approx. every 2-4 hours | As needed |

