| BHB (mmol/L) | At presentation and every 6 hours until ≤ 1.0 | 12-18 hours after d/c of IV insulin* As needed for POC glucose $> 300 \times 2$ |
| UA | At presentation | If POC glucose > 300 mg/dL x 2 |
| CGM | Placed at time of enrollment | Wear x 1 week |

BMP = basic metabolic panel; VBG = venous blood gas; BHB = beta-hydroxybutyrate; DKA = diabetic ketoacidosis; CGM = continuous glucose monitor; IV = intravenous; POC = point-of-care; HbA1c = hemoglobin A1c; * for those participants who remain hospitalized after 24 hours.

C.2.3. For participants who consented to wear a CGM (if study funding allows):

- New onset participants: the CGM sensor will be removed either by the participant/family or if needed by clinical staff at the routine 1 week follow-up visit at the Barbara Davis Center (BDC). The device will then be returned to the study team for data download.
- Established participants with type 1 diabetes: these participants will be provided with supplies to mail the CGM to study personnel at the Barbara Davis Center after wearing it for 1 week or will have the option to return the CGM to the BDC in person in 1 week.
- If the CGM sensor malfunctions or becomes disconnected after discharge from the hospital prior to the 1 week time frame the participant will be asked to return the CGM to study personnel at the Barbara Davis Center for data download either by mail (see above) or at their routine 1 week follow-up visit.

C.3. Funding: We have secured small study funds through the Children's Diabetes Foundation (Barbara Davis Center) to cover the cost of the CGMs and Research Assistant (recruitment and consenting) compensation. However, this protocol can be implemented without funding if needed as the essential components (primary outcomes) are not dependent on funding. The laboratory testing required to assess our primary outcomes falls under standard-of-care management for DKA. Further, wearing a CGM is an optional part of the study and many of our secondary outcomes can be assessed without CGM use if needed. Further, departmental funds through the Barbara Davis Center will be available to cover small unanticipated costs.

D. Description, Risks and Justification of Procedures and Data Collection Tools:

Participant Data: In order to investigate our primary and secondary outcomes we will collect the following Protected Health Information (PHI) from the study participant:

- Standard medical history, name, date of birth, race, and diagnosis.

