5. **Subcutaneous insulin injection:** Insulin will be administered subcutaneously during the hospitalization by trained clinical staff with experience in subcutaneous medication dosing. Further, the dose of subcutaneous insulin will be determined by the primary Diabetes Team and/or the PI. Once discharged from the hospital, the participant will be told to contact the Barbara Davis Center with any issues or concerns at home.
6. **CGM:** Wearing a CGM will be optional to study participants. Additionally, the CGM sensor will be placed by trained study personnel to reduce risk of injury and/or sensor malfunction and to improve compliance. The area where the sensor is to be placed will be cleaned with an isopropyl alcohol solution prior to placement to reduce any risk of infection at the site.

V. Adverse Event Reporting:

Adverse events and/or unanticipated problems will be recorded in a log for tracking purposes. Unanticipated problems will be reported to the IRB within 10 business days of knowledge of the

event. Severe or serious adverse events will be reported to the IRB immediately. Adverse events include:

1. Severe hypoglycemia (blood glucose < 70 mg/dL resulting in seizure, need for glucagon injection, or need for IV dextrose bolus).
2. Cerebral edema (requiring treatment with IV mannitol or IV 3% hypertonic saline).
3. Recurrent ketogenesis (serum beta-hydroxybutyrate > 2.0 mmol/L after discontinuation of IV insulin).
4. Infection or allergic reaction at CGM insertion site.

Criteria to pause or stop the study protocol:

Study protocol will be halted or stopped if:

- Patients in the study group experience a disproportionate number of severe hypoglycemic events than those in the control group.
- Patients in the study group experience a disproportionate number of cerebral edema events than those in the control group.
- A significant number of patients (greater than 30 %) develop skin infections at the CGM site requiring antibiotic treatment.
- Participants in the control group experience a disproportionate number of recurrent DKA events requiring treatment with IV insulin after initial resolution.

VI. Potential Scientific Problems:

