In any clinical study unforeseen human factors provide challenges. This current study is based on a previous study in adults (14) with no reported adverse events such as increased hypoglycemia in those given glargine early in DKA management. However, the primary physician or Diabetes Team may decide to change the participant’s DKA management plan and they would, therefore, come off the study protocol. Additionally, the accuracy of a CGM (which samples interstitial fluid) when used in states of dehydration has not been well-studied. However, a number of small studies have shown CGM to be an accurate measure of blood glucose in an ICU setting (21,25). To improve CGM accuracy we will place the CGM only after initial intravascular hydration has been completed and the CGM will be calibrated (if needed) using a POC glucometer at least twice daily. Additionally, we will continue to obtain frequent POC glucometer readings throughout the hospitalization as this will be used to measure our primary outcome.

We have also performed careful power calculations to allow meaningful analyses of our data.

VII. Data Analysis Plan:

Table 1: Power calculations:

| | | | | | |
|---------------------------|-------|-------|-------|-------|-------|
| Significance level | 0.05 | 0.05 | 0.05 | 0.05 | 0.05 |
| Effect size (%) | 20 | 25 | 30 | 40 | 50 |
| Odds Ratio | 2.333 | 2.852 | 3.500 | 5.444 | 9.333 |
| Power (%) | 80 | 80 | 80 | 80 | 80 |
| Total N | 186 | 122 | 84 | 48 | 30 |

Per our power analysis (Table 1), with a total sample size of 48-50 (24-25 per group) we will have 80% power to detect an absolute difference of 40% in rebound hyperglycemia between the two study groups. These power analyses assume that 30% of participants in the early glargine group will experience rebound hyperglycemia. Chi-squared tests will be employed to evaluate whether the difference in rebound hyperglycemia between the two study groups is statistically significant. We will also use logistic regression to adjust for potential confounders (*BMI, sex, age, established T1D versus newly-diagnosed T1D*). Using a blocked and stratified randomization plan we expect to have similar numbers of newly-diagnosed T1D and known T1D patients in each group.

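### Recurrent ketogenesis (Aim 2) counts ketosis that had not cleared when IV insulin stopped, and detection of later recurrence depends partly on glucose

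*Combined protocol and SAP*

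**What the plan says.** **Outcome.** Specific Aim 2 is "To evaluate the rate of recurrent ketogenesis (beta-hydroxybutyrate ≥ 1.5 mmol/L within 12 hours after discontinuation of IV insulin". Secondary outcome 2 in IV.A has the same threshold and window, ending at discharge if that comes first. Section V lists as an adverse event "Recurrent ketogenesis (serum beta-hydroxybutyrate > 2.0 mmol/L after discontinuation of IV insulin". None of the three requires BHB to have been low beforehand.

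**Stop rule.** IV.C.2.2 moves a child to subcutaneous insulin "When venous pH ≥ 7.3 and serum bicarbonate ≥ 18 mmol/L (or BHB < 1.0 mmol/L) and participant is awake and alert". The control-group text in IV.C.2.1 has the same structure: BHB is an alternative to bicarbonate, not an added requirement.

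**BHB on the infusion.** "Serum beta-hydroxybutyrate (BHB) will be obtained at presentation and then every 6 hours while on IV insulin until" it reaches 1.0 mmol/L or less (IV.C.2.1). Venous pH and electrolytes are drawn every 2-4 hours. The visible text asks for no BHB at the moment the infusion stops.

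**BHB after the infusion.** The IV.C.2.2 text reads "Serum BHB obtained every 6 hours until ≤ 1.0 mmol/L or at any time if blood glucose on glucometer is > 300 mg/dL" on two consecutive measurements. It adds: "Participants who remain hospitalized over 24 hours will have a BHB drawn at 12-18 hours after discontinuation of IV insulin". The summary table at the end of IV.C.2.2 lists for the post-resolution period only "12-18 hours after d/c of IV insulin* As needed for POC glucose" above 300 mg/dL twice, with the first item limited to children still in hospital after 24 hours. Its 6-hourly schedule appears only in the column for DKA treatment.

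Figure 1 and the hospital guideline cited in IV.D are not available here, so this point concerns the visible text.

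**The concern.** Hypothesis 2 says early glargine reduces *recurrent* ketogenesis: ketosis that returns after it has gone. The rule as written measures any ketosis after the stop. There are two consequences.

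1. A child who stops on pH and bicarbonate with BHB still raised, and is next measured at 1.5 or above, is an event although nothing recurred. If this is equally common in both arms, it mislabels events and dilutes a real difference. If it is unequal, it creates an arm difference that may be a genuine effect on post-stop ketosis but is not evidence about recurrence. The documents do not settle the direction: the Background cites a paediatric review with faster acidosis correction under early glargine and other work with no difference.

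2. A child who has cleared is looked at again inside the window only if glucose is high twice. If Hypothesis 1 is right, that trigger fires less often under early glargine, so more recurrences could go unseen in that arm, which would favour Hypothesis 2.

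**Working it through.** **The plan's own figure.** The Data Analysis Plan assumes, for the primary outcome, "These power analyses assume that 30% of participants in the early glargine group will experience rebound hyperglycemia", with a 40-point difference and hence 70% in controls. The odds ratio is (0.70/0.30)/(0.30/0.70) = 5.444, as stated. With pooled variance and two-sided 0.05, n per arm = [1.960 × √(2 × 0.5 × 0.5) + 0.842 × √(0.21 + 0.21)]² / 0.40² = 23.3, so 24 per arm and 48 in total, as stated. No BHB quantity enters. No figure and no test is given for recurrent ketogenesis.

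**The definitions applied to BHB sequences** (illustrative values in mmol/L, first value at the stop):

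| Sequence | Plan as written | Requiring a prior BHB ≤ 1.0 | Requiring a prior BHB < 1.5 |
|---|---|---|---|
| 2.2, 1.7, 0.8 | recurrent | persistent | persistent |
| 1.6, 1.4, 1.5 | recurrent | persistent | recurrent |
| 1.2, 2.5 | recurrent | persistent | recurrent |
| 0.8, 1.8 | recurrent, if the 1.8 is drawn | recurrent | recurrent |

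**Who is tested after the stop.** The IV.C.2.2 text has two readings. If the 6-hourly series ends at the first value of 1.0 or less, whenever that occurs, a child cleared on the infusion has no scheduled draw in the window. If the series starts afresh at resolution, every child still in hospital gets at least one. The summary table leans against the second reading. On either reading, a child measured at 1.0 or less after the stop is re-tested within 12 hours only on the glucose trigger. The 12-18 hour draw meets the window only at hour 12, and only in children who stay over 24 hours.

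**Size of the labelling problem** (all rates assumed). Let u be the share counted only because BHB had not cleared, and r the recurrence rate in the rest, with every recurrence seen.

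- Share of counted events that are not recurrences = u / [u + (1 − u)r]. Lowest, u = 5% and r = 20%: 0.05/0.24 = 21%. Highest, u = 25% and r = 10%: 0.25/0.325 = 77%.
- Equal u, true recurrence 10% versus 30%: observed difference = (1 − u) × 20 points, which is 19 points at u = 5% and 15 at u = 25%. If the uncorrected chi-squared test were used with 24 per arm, exact power falls from 0.43 (u = 0) to 0.35 and 0.20.
- Unequal u, equal r: gap = (difference in u) × (1 − r). For 10% versus 5% it is 4.5 points (r = 10%) or 4.0 points (r = 20%). For 15% versus 5% it is 9 or 8 points, about 2 of 24 children.

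**How plausible is u?** Assume BHB falls at k = 0.2-0.5 mmol/L per hour and the next draw is equally likely at any time in the 6 hours after the stop. A child stopping at B is then counted with probability (B − 1.5)/(6k), capped at 1. For B = 2.2 this is 0.7/3.0 = 23% to 0.7/1.2 = 58%. For B = 3.0 it is 1.5/3.0 = 50% to 100%. So u = 25% needs 25-50% of children to stop at about 3.0; u = 5% needs 5-10%.

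**Glucose trigger** (assumed). Take the plan's rebound rates and suppose half of rebound children have two consecutive values above 300. The trigger then reaches 0.5 × 30% = 15% versus 0.5 × 70% = 35%. Let q be the share of recurrences found whatever the trigger's arm-specific rate, either because the child is still on 6-hourly draws or because the recurrence always comes with two high values. With equal true rates, the control-to-early ratio of detected recurrences is [q + (1 − q)0.35] / [q + (1 − q)0.15]: 1.41 at q = 0.25, 1.17 at q = 0.5 and 1.00 at q = 1. The extreme q = 0 gives 2.33.

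**The case against.** **The threshold is explicit and identical in both randomised arms, so this is labelling.** In part. The comparison of BHB ≥ 1.5 after the stop is legitimate as a comparison of post-stop ketosis. It does not answer Hypothesis 2, which is about recurrence.

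**The text under the post-resolution heading may give every child one draw.** This stands as a real ambiguity. It narrows the surveillance gap to recurrences after a cleared post-stop value but does not close it.

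**Children not yet at 1.0 stay on 6-hourly draws, and the Background says rebound hyperglycemia can lead to ketogenesis.** Both stand. The trigger governs only part of the cohort, and recurrences may tend to come with high glucose. Hypothesis 1 also concerns values above 180 mg/dL; no document gives rates of two consecutive values above 300.

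**The stronger reading.** A reader might infer that most recurrences go unseen and that controls will show over twice as many at equal true rates. The documents do not support that. The 2.33 ratio needs every non-persistent child to be off scheduled draws and recurrence to be independent of glucose.

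**Figure 1 or the hospital guideline may add draws.** Possible, and not checkable here. Extra draws would ease the surveillance gap but would not supply the missing clearance condition in the outcome definitions.

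**Conclusion.** The point holds for a secondary outcome and should be fixed. On the visible text it is certain that uncleared ketosis can be scored as recurrence, in Aim 2 and in the adverse-event log, and that a child at 1.0 or less is re-tested in the window only on the glucose trigger. Whether every child has one post-stop draw is unclear.

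The size is unknown because the plan gives no BHB rates. The 21-77% range rests on the assumed u and r, and its upper end needs a quarter to a half of children to stop near BHB 3.0, which nothing in the documents supports. The trigger bias runs from nil upward, and its direction favours Hypothesis 2 only if two values above 300 are rarer under early glargine.

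A reader might also infer that the trial's main result is compromised. It is not: rebound hyperglycemia, N = 48 and its power do not use BHB.

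**What to change.** Leave the clinical stop rule unchanged.

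1. **IV.A, definition.** Count as *recurrent* a BHB ≥ 1.5 within 12 hours after the stop (or to discharge) that follows a documented BHB ≤ 1.0, the plan's own clearance threshold, before, at or after the stop. Label any other post-stop BHB ≥ 1.5 *not cleared/persistent*.
2. **VII, analysis.** Test Hypothesis 2 on *recurrent* in all analysed children and name the test. Report persistent and total post-stop BHB ≥ 1.5 by arm beside it, since a child with persistent ketosis has less chance of being scored recurrent. Add a sensitivity analysis with < 1.5 as the clearance threshold, which picks up rises such as 1.2 to 2.5.
3. **V.** Keep logging every BHB > 2.0, labelled by the same split.
4. **IV.C.2.2 and its summary table.** State that BHB is drawn at the stop and at about 6 and 12 hours, or at discharge if earlier, in every child whatever the glucose, with one assay method for the post-stop draws.

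Items 1-3 need no new test. Item 4 adds at most three small BHB tests per child (3 × 48 = 144), some already scheduled, and IV.D already provides for BHB by point-of-care meter. Item 4 has to be in place during enrolment, because values never drawn cannot be recovered in analysis.

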- Upon diagnosis of DKA patients will begin rehydration with standard fluid therapy using an initial IV bolus of 10mL/kg of 0.9% saline.
- Fluid boluses may be repeated at the discretion of the treating physician to restore hemodynamic instability.
- During initial therapy, study personnel will obtain informed consent. .
- Participant Data: basic information such as name, date of birth, race/ethnicity, and diagnosis will be collected.
- Randomization:
 - We will use a blocked, stratified randomization scheme to allocate participants 1:1 to treatment groups. Randomization will be stratified within new onset and existing T1D patients to ensure balance across treatment groups.
 - Ideally, randomization will occur during the initial fluid bolus, however, if this is not possible then the patient will be treated with the standard DKA protocol for this study site until consent is completed, but not beyond the time frame outlined in the exclusion criteria.
 - Participants will be randomized into one of two groups:
 - 1. Early glargine, study group (N ~ 25):**
 - a. Administer glargine SQ x 1 when pH \geq 7.10.
 - b. Primary investigator and/or on-call co-investigator to determine glargine dose:
 - i. New onset T1D: 0.3 units/kg
 - ii. Established T1D: use home total daily dose (TDD) of long-acting insulin (or TDD of basal if on an insulin pump), converted to glargine equivalents.
 - 2. Standard-of-care, control group (N ~ 25):**
 - a. Administer glargine SQ x 1 at time of correction of acidosis (venous pH \geq 7.3 and serum bicarbonate \geq 18 or BHB \leq 1) and discontinuation of IV insulin.
 - b. Primary investigator and/or on-call co-investigator to determine glargine dose as described above.
- After initial fluid bolus(es), standard insulin therapy begins with a continuous infusion of IV regular insulin at a rate of 0.1 units/kg/hr.
- Ongoing rehydration is established using IV fluids with $\frac{3}{4}$ normal saline at a standard rate of 1.5 x maintenance unless this is determined to be harmful by the primary attending physician.
- Potassium replacement is provided using IV fluids containing potassium acetate and potassium phosphate.
- When serum glucose concentration declines below 250 mg/dL, dextrose (5-12.5%) is added to the IV fluids to maintain serum glucose between 100 mg/dL and 200 mg/dL.

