- Lab collection: serum glucose, serum bicarbonate, serum sodium, serum chloride, serum potassium, serum blood urea nitrogen, serum creatinine, and serum beta-hydroxybutyrate will be obtained using standard venipuncture methods per hospital policy by trained staff. These measurements will be determined using standard methods in the Children's Hospital Colorado core laboratory. Blood glucose and beta-hydroxybutyrate will also be obtained using a point-of-care meter per hospital policy or at the Barbara Davis Center.

DKA protocol: Aside from the timing of glargine administration, all other treatment of DKA will be per the standard hospital DKA protocol (clinical care guidelines) at Children's Hospital Colorado. Available at: <https://ccguidelinesportal.childrenscolorado.org/guidelines/>

Glargine administration: This is a long-acting insulin analog which could theoretically increase the risk of hypoglycemia during its duration-of-action (20-24 hours). However, this is standard therapy for type 1 diabetes management with a long history of safe use. As such, study participants will receive glargine regardless of which study group they are randomized to; the only difference being the timing of glargine administration. Further, one of our secondary outcomes is to determine the risk of hypoglycemia between those given glargine early in DKA management versus those given glargine at time of DKA resolution.

CGM data collection: Wearing a CGM will be optional for study participants and included in the protocol as funding allows. The CGM sensor will be placed by trained study personnel to reduce risk of injury and/or sensor malfunction and to improve compliance. The CGM data will be downloaded after 1 week using standard industry software by trained staff or study personnel and the information stored in a locked study office.

Plan to minimize risk:

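### No listed pause or stop criterion covers an excess of recurrent DKA in the early glargine group, because the recurrent-DKA criterion names only the control group

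*Combined protocol and SAP*

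**What the plan says.** The list under Criteria to pause or stop the study protocol (Section V, Adverse Event Reporting) has four entries:

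- Severe hypoglycemia: "Patients in the study group experience a disproportionate number of severe hypoglycemic events than those in the control group".
- Cerebral edema: "Patients in the study group experience a disproportionate number of cerebral edema events than those in the control group".
- CGM-site infection: "A significant number of patients (greater than 30 %) develop skin infections at the CGM site requiring antibiotic treatment". This entry is not tied to an arm and is the only one with a number.
- Recurrent DKA: "Participants in the control group experience a disproportionate number of recurrent DKA events requiring treatment with IV insulin after initial resolution".

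The randomization list in C.2.1 defines the study group as early glargine and the control group as standard of care, about 25 in each.

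Two other parts of Section V apply to both arms. Recurrent ketogenesis (BHB above 2.0 mmol/L after IV insulin stops) is a named adverse event, and severe or serious adverse events are reported to the IRB at once. Neither is linked to a pause.

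On the expected direction, Hypothesis 2 states: "Early administration of glargine in the treatment of DKA in children will result in a reduced rate of recurrent ketogenesis". Section III says no data exclusively in children show whether early glargine protects against recurrent ketogenesis.

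**The concern.** Two of the three between-arm criteria look for harm in the experimental arm. The third, on recurrent DKA, looks only at controls. It is the only one of the four entries that leaves the experimental arm unwatched, and its event is closely related to an outcome on which the trial is testing the treatment.

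A safety rule should not depend on the answer to an open question. If early glargine turned out to be followed by more recurrent DKA, investigators working from the written list would find no entry telling them to pause. What is at stake is a stated safety trigger for children in the experimental arm of a small trial.

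**Working it through.** **1. Which arm each criterion watches.**

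| Event | Excess that counts | Early glargine arm covered? |
|---|---|---|
| Severe hypoglycemia | Study group over control | Yes |
| Cerebral edema | Study group over control | Yes |
| CGM-site infection | Over 30% of patients, any arm | Yes |
| Recurrent DKA needing IV insulin | Control group | No |

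No other section supplies a pause criterion for recurrent DKA.

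**2. The plan's own figure.** The criterion has no number to reproduce. The only relevant figure is the sample size in Section VII, which sets the arm size used below. With 30% v 70%, two-sided alpha 0.05, 80% power and pooled variance:

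n per arm = [1.96·√(2·0.5·0.5) + 0.8416·√(0.3·0.7 + 0.7·0.3)]² / 0.4² = (1.386 + 0.545)² / 0.16 ≈ 23.3, so 24 per arm and 48 in total. This matches Table 1 of Section VII. The text allows 24-25 per group.

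**3. Scale of a lopsided split.** With equal arms and all 5 events in one arm, the two-sided Fisher p is 2·C(n,5)/C(2n,5).

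- n = 24: 2 × 42,504 / 1,712,304 = 0.0496.
- n = 25: 2 × 53,130 / 2,118,760 = 0.0502.

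The result crosses 0.05 when one participant per arm is added, so it shows scale and is not a threshold. The protocol does not say that a p-value defines *disproportionate*.

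**4. What a one-way rule gives up.** This step is illustration only, because the documents give no recurrent-DKA rate and no threshold. Assume 25 per arm, one look at the final counts, and a rule that fires at an excess of at least k events. Let C and S be independent binomial counts in the control and early glargine arms. The one-way rule fires if C − S ≥ k, and the two-way rule fires if |C − S| ≥ k.

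| Assumed true rates, control v early | k | One-way | Two-way |
|---|---|---|---|
| 5% v 20% | 3 | 0.0020 | 0.7075 |
| 5% v 20% | 4 | 0.0004 | 0.5364 |
| 5% v 20% | 5 | 0.0001 | 0.3629 |
| 20% v 5% | 4 | 0.5360 | 0.5364 |
| 5% v 5% | 3 | 0.0495 | 0.0989 |
| 5% v 5% | 4 | 0.0124 | 0.0247 |
| 5% v 5% | 5 | 0.0025 | 0.0049 |

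When the excess is in the early arm, the one-way rule almost never fires. When it is in the control arm, the two rules perform alike. With equal rates, the two-way rule doubles a chance that is small at k = 4 or 5 and reaches about 0.10 at k = 3.

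**5. Is recurrence in the early arm possible on the protocol's own figures?** Section IV.D gives glargine a duration of action of 20-24 hours. Controls receive it when IV insulin stops, while the early arm receives it once pH is at least 7.10. Let X be the hours from the early dose to the end of the infusion. The action left after the infusion is then 20 − X to 24 − X hours in the early arm, against 20-24 in controls. The documents do not give X. Over an assumed 4 to 12 hours, the remainder runs from 16-20 hours down to 8-12 hours. It would end inside the 12-hour outcome window only if X exceeded 8 hours (for a 20-hour action) or 12 hours (for a 24-hour action). This shows possibility, not expectation.

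**The case against.** The strongest reply is that the listed criteria are not the only safeguard. Section V does not call its list exhaustive. Serious adverse events from both arms reach the IRB immediately, and recurrent ketogenesis is logged in both arms. A reader might infer that an excess in the early arm could never lead to a pause. The documents do not support that, because the IRB would see serious events and could act. What stands is narrower: the protocol attaches no pause to that report, although it does write pause criteria for other between-arm comparisons.

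Second, the direction may be deliberate, to protect controls if early glargine works. It may also be a drafting slip. A reader might infer that it was chosen to suit the hypothesis, but Section V gives no reason. A two-way criterion keeps the protection of controls in any case.

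Third, the hazard is not demonstrated. Both arms receive subcutaneous lispro after transition (C.2.2). The background describes continuing long-acting insulin as a way to reduce rebound and ketogenesis, and cites less rebound in adults. This is a fair caution against reading step 5 as a prediction. It does not close the question in children, for whom Section III says data are lacking. The protocol itself schedules a BHB at 12-18 hours for those still in hospital after 24 hours, in both arms.

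Fourth, *disproportionate* has no number, and no one is named to judge it or when. That is true of all three between-arm criteria and is a separate weakness. Defining the word would not bring the early glargine arm under this criterion.

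**Conclusion.** The point holds for the criteria as listed: none covers an excess of recurrent DKA in the early glargine group. That rests on the text alone and needs no assumption.

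Its size cannot be fixed from the documents. A reader might infer that 5 recurrences on control against 0 on early glargine would trigger the pause while the reverse would not. The first half of that is unsupported, because no threshold is stated. The firing probabilities depend on assumed rates, an assumed threshold and a single look. The dose-timing argument depends on an interval the protocol does not give. Hypothesis 2 concerns BHB rather than DKA needing IV insulin, so it is a related question and not the same event.

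The change is worth making because it closes a gap in a stated safety rule at very little cost.

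**What to change.** In the recurrent-DKA criterion, replace the reference to the control group with a reference to either group compared with the other, and leave the event definition as it is. If the sponsor means to cover controls only, the protocol should say so and give the reason.

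The edit is one phrase and needs no new data, because both arms follow the same post-infusion monitoring schedule. The downside is a higher chance of a false pause: 0.012 to 0.025 under the assumed rule of 4 excess events with equal 5% rates, and 0.05 to 0.10 if the rule were 3.

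As a separate matter, the sponsor should state how *disproportionate* is judged, by whom and when. Until then, none of the three between-arm criteria can be applied consistently, and this edit alone does not change that.
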